5.3.2 Biomicroscopy Findings/Slit Lamp Examination

Biomicroscopy assessment will be performed at all study visits, including Visit 1 to 6 and unscheduled visits. The reporting unit for each biomicroscopy finding will be *eye*.

A summary of grade category counts and percentages will be presented for each parameter at each scheduled visit and all unscheduled visits combined. A listing of "Other" slit lamp findings will also be provided.

Additionally, for each biomicroscopy parameter, counts and percentages of eyes that experience an increase of ≥ 2 grades from baseline (Visit 1) to any subsequent visit will be presented, together with a supportive listing.

5.3.3 Device Deficiencies

A frequency table showing counts for each treatment-emergent Device Deficiency category will be presented. In addition, listings for treatment-emergent and pre-treatment device deficiencies will be provided.

The table content is completely redacted with black bars. It appears to be a frequency table with multiple rows and columns, but no data is visible.

[REDACTED]

[REDACTED]

[REDACTED]

[REDACTED]	[REDACTED]	[REDACTED]	[REDACTED]
[REDACTED]	[REDACTED]	[REDACTED]	[REDACTED]

[REDACTED]

- [REDACTED]
- [REDACTED]

- [REDACTED]
 - [REDACTED]
 - [REDACTED]
 - [REDACTED]
 - [REDACTED]
 - [REDACTED]
 - [REDACTED]
 - [REDACTED]
 - [REDACTED]

- [REDACTED]
- [REDACTED]
- [REDACTED]

8 Sample Size and Power Calculations

Sample size is based upon the following:

- Premarket Notification (510(k)) Guidance Document for Daily Wear Contact Lenses – at least 50 evaluable subjects to be followed for at least 3 months, for claim of substantial equivalence for a lens with different repeating monomer Units (new Parent USAN). In addition, a 2:1 ratio in Test vs Control evaluable subject allocation should be adopted.
- ISO 11980:2012 – 50 completed subjects in Test, for 3 months. Either 2:1 or 1:1 ratio of Test to Control can be accepted.

9 References

1. Premarket Notification (510(k)) Guidance Document for Daily Wear Contact Lenses
2. ISO 11980:2012 Ophthalmic optics - Contact lenses and contact lens care products - Guidance for clinical investigations

10 Revision History

This is the first revision (Version 2.0) of the Statistical Analysis Plan for this study. This version of the Statistical Analysis Plan is based on Version 2.0 of the study protocol.

SAP Section	Information Changed
[REDACTED]	[REDACTED]
Title page (page 1)	Administrative: to update author's name and credential

11 Appendix

Table 11-1 Schedule of Study Procedures and Assessments

Procedure/ Assessment	Visit 1 Screening/ Baseline/ Dispense	Visit 2 Week 1 Follow-up ⁵	Visit 3 Week 2 Follow-up ⁵	Visit 4 Month 1 Follow-up ⁵	Visit 5 Month 2 Follow-up ⁵	Visit 6 Month 3 Follow- up/Exit ⁵	Early Exit	USV
	Day 1	Day 8 (-2/+2 days)	Day 15 (-3/+3 days)	Day 30 (-3/+5 days)	Day 60 (-3/+5 days)	Day 95 (-3/+5 days)		
Informed Consent	X							
Demographics	X							
Medical History	X	X	X	X	X	X	X	(X)
Concomitant Medications	X	X	X	X	X	X	X	(X)
Inclusion/Exclusion	X							
Habitual lens information (brand/manufacturer, power, modality/wear success, habitual lens care brand)	X							
VA w/ habitual correction (OD,OS Snellen distance)	X					X	X	(X)
Manifest refraction ⁴	X	(X)	(X)	(X)	(X)	X	X	(X)
BCVA ⁴ (OD,OS Snellen distance with manifest refraction)	X	(X)	(X)	(X)	(X)	X	X	(X)
	■					■	■	■
Biomicroscopy	X	X	X	X	X	X	X	(X)
	■							

Printed By:

Print Date:

Procedure/ Assessment	Visit 1 Screening/ Baseline/ Dispense	Visit 2 Week 1 Follow-up ⁵	Visit 3 Week 2 Follow-up ⁵	Visit 4 Month 1 Follow-up ⁵	Visit 5 Month 2 Follow-up ⁵	Visit 6 Month 3 Follow-up/Exit ⁵	Early Exit	USV
	Day 1	Day 8 (-2/+2 days)	Day 15 (-3/+3 days)	Day 30 (-3/+5 days)	Day 60 (-3/+5 days)	Day 95 (-3/+5 days)		
Randomize and record lens power	X							
[REDACTED]	■							
Order study lenses*	X							
IP Dispense*	X	X	(X)	(X)	(X)			(X)
VA w/ study lenses (OD, OS Snellen distance) ¹	X	X	X	X	X	X	X	(X)
[REDACTED]		■	■	■	■	■	■	■
[REDACTED]	■	■	■	■	■	■	■	■
[REDACTED]	■	■	■	■	■	■	■	■
[REDACTED]	■	■	■	■	■	■	■	■
[REDACTED]		■	■	■	■	■	■	■

Printed By:

Print Date:

Procedure/ Assessment	Visit 1 Screening/ Baseline/ Dispense	Visit 2 Week 1 Follow-up ⁵	Visit 3 Week 2 Follow-up ⁵	Visit 4 Month 1 Follow-up ⁵	Visit 5 Month 2 Follow-up ⁵	Visit 6 Month 3 Follow- up/Exit ⁵	Early Exit	USV
	Day 1	Day 8 (-2/+2 days)	Day 15 (-3/+3 days)	Day 30 (-3/+5 days)	Day 60 (-3/+5 days)	Day 95 (-3/+5 days)		
[REDACTED]	■	■	■	■	■	■	■	■
[REDACTED]	■	■	■	■	■	■	■	■
[REDACTED]	■	■	■	■	■	■	■	■
[REDACTED]	■	■	■	■	■	■	■	■
[REDACTED]	■	■	■	■	■	■	■	■
AEs	X	X	X	X	X	X	X	(X)
Device deficiencies	X	X	X	X	X	X	X	(X)
Exit Form	(X)	(X)	(X)	(X)	(X)	(X)	X	(X)

USV = Unscheduled Visit
 *source only

[REDACTED]

⁵All follow-up visits should be scheduled at least 4 hours after lens insertion.

[REDACTED]

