1.2 Study Description

Key components of the study are summarized in Table 1-1.

Table 1-1 Study Description Summary

Study Design	Prospective, multi-center, randomized, [REDACTED] controlled, double-masked, parallel-group
Study Population	
Volunteer subjects aged 18 or over who are adapted daily wear frequent replacement soft contact lens wearers, excluding Biofinity habitual wearers, have at least 3 months of soft contact lens wearing experience, and who wear their habitual lenses at least 5 days per week and at least 8 hours per day.
 
Subjects must require contact lens correction in a sphere power range from -1.00 to -6.00 D. [REDACTED] [REDACTED] [REDACTED]
 
Target to complete: 90 subjects (60:30; Test:Control) Planned to enroll: ~120 subjects

Number of Sites	~8 (US)
Test Product	[REDACTED] soft contact lenses [REDACTED]
Control Product	CooperVision® BIOFINITY® (comfilcon A) soft contact lenses (Biofinity)
Duration of Treatment	Approximately 3 months
Visits	
Visit 1: Screening/Baseline/Dispense (Day 1) Visit 2: Week 1 Follow-up (Day 8 -2/+2 days) Visit 3: Week 2 Follow-up (Day 15 -3/+3 days) Visit 4: Month 1 Follow-up (Day 30 -3/+5 days) Visit 5: Month 2 Follow-up (Day 60 -3/+5 days) Visit 6: Month 3 Follow-up/Exit (Day 95 -3/+5 days)

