1.3 Randomization

A member of the Randomization Programming group at Alcon who is not part of the study team will generate the randomized allocation schedule(s) for study lens assignment.

[REDACTED]

Subjects will be randomized in a 2:1 ratio to receive either [REDACTED] or Biofinity contact lenses, respectively. [REDACTED]

[REDACTED]

[REDACTED]

Randomization schedule will be blocked to ensure a balance (2:1) in lens allocation within sites.

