4.6 Interim Analysis for Effectiveness

No interim analysis is planned for effectiveness endpoints.

5 Safety Analysis Strategy

Unless otherwise specified, separate summary tables will be presented for the Completed and the Discontinued analysis sets with the following distinction:

- Completed Control (eyes/subjects)
- Completed Test (eyes/subjects)
- Discontinued Control (eyes/subjects)
- Discontinued Test (eyes/subjects)

Subjects/eyes will be categorized under the actual lens exposed.

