5.3 Statistical Methods for Safety Analyses

5.3.1 Adverse Events

The applicable definition of an AE is in the study protocol. All AEs occurring from when a subject signs informed consent to when a subject exits the study will be accounted for in the reporting. Analysis and presentation of pre-treatment AEs will be separated from treatment-emergent AEs occurring during the study period. A pre-treatment AE is an event that occurs after signing informed consent but prior to exposure to the study lens (not including trial fitting lenses). The period for treatment-emergent AE analysis starts from exposure to study lens until the subject completes or is discontinued from the study.

Descriptive summaries (counts and percentages) for ocular and nonocular AEs will be presented by Medical Dictionary for Regulatory Activities (MedDRA) Preferred Terms (PT). Serious AEs and significant non-serious ocular AEs will be noted. Additionally, relationship to lens will be identified in all AE tables. Unit of presentation for ocular AEs will be eye and nonocular AEs will be subject.

Individual subject listings will be provided for both pre-treatment and treatment-emergent AEs, where any AE leading to study discontinuation will be indicated.

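### Does the device deficiency table in SAP 5.3.3 need a stated unit and percentages, given 2:1 allocation?

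*SAP*

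**What the plan says.** Device deficiencies are one of three safety endpoints (Protocol 12.6, SAP 5.1). For them SAP 5.3.3 states: "A frequency table showing counts for each treatment-emergent Device Deficiency category will be presented". It adds that "listings for treatment-emergent and pre-treatment device deficiencies will be provided". Protocol 12.6 is no fuller: it promises a frequency per category and a supporting listing.

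The other two safety endpoints are described more closely. SAP 5.3.1 plans "Descriptive summaries (counts and percentages) for ocular and nonocular AEs" and fixes the unit: "Unit of presentation for ocular AEs will be eye and nonocular AEs will be subject". SAP 5.3.2 sets the eye as the unit and states: "A summary of grade category counts and percentages will be presented for each parameter".

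The opening of SAP section 5 sets a default for all safety tables: "separate summary tables will be presented for the Completed and the Discontinued analysis sets with the following distinction". The four groups that follow are Completed Control, Completed Test, Discontinued Control and Discontinued Test. Each carries a generic eyes/subjects label, and grouping follows the lens actually worn. Nothing in 5.3.3 overrides this.

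**The concern.** Safety in this trial is purely descriptive, so the tables are what a reader has for comparing the two lenses. Under 2:1 allocation, bare counts mislead if read straight across: equal performance looks like twice as many faults on the test lens, and equal counts hide a control rate twice as high. If dropout differs between arms, the ratio of group sizes also moves away from 2:1 in the Completed and Discontinued tables, so halving the test count is not a safe correction.

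The unit is also open. One subject may report several torn lenses, so a number of deficiencies divided by the number of subjects is not the proportion of subjects affected. Since the SAP settles both matters for the other two safety endpoints, their absence here looks like an oversight.

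**Working it through.** **Inputs.** About 120 subjects planned, with about 80 test and 40 control (Protocol section 3); 2:1 randomization (SAP 1.3); target of 90 completing, 60 test and 30 control (SAP Table 1-1). The documents give no expected deficiency rate, so the rates below are assumptions.

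**Group sizes reproduce.** 120 × 2/3 = 80 and 120 × 1/3 = 40. 90 × 2/3 = 60 and 90 × 1/3 = 30.

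**Effect of allocation on counts.** With the same share r of subjects affected in each arm and one deficiency each, expected counts are 80r and 40r as assigned, or 60r and 30r among completers:

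| r | Assigned, test v control | Completers, test v control |
|---|---|---|
| 5% | 4 v 2 | 3 v 1.5 |
| 10% | 8 v 4 | 6 v 3 |
| 20% | 16 v 8 | 12 v 6 |

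In the other direction, counts of 4 v 4 are 4/80 = 5% and 4/40 = 10%.

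**The 2:1 ratio is only an expectation.** With 6 deficiencies in total and equal rates, the test count is about Binomial(6, 2/3). Test exceeds control with probability 496/729 = 0.68, they tie with 160/729 = 0.22, and control exceeds test with 73/729 = 0.10.

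**Uneven dropout.** Suppose 120 − 90 = 30 dispensed subjects do not complete. Splits between test and control give:

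- 20/10: Completed 60:30 = 2.0, Discontinued 20:10 = 2.0
- 24/6: Completed 56:34 = 1.65, Discontinued 24:6 = 4.0
- 16/14: Completed 64:26 = 2.46, Discontinued 16:14 = 1.14

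These splits only illustrate the point. Enrolled means consented, and the Discontinued set holds dispensed subjects only, so some of the 30 may be screen failures. The example shows that each group's own N is needed.

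**Unit.** Eight test-arm deficiencies could be 8/80 = 10% of subjects or, if all came from one person, 1/80 = 1.25%.

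**Can the rate be recovered from planned output?**

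- Numerator: the table gives counts by category, and the listings let repeats within a subject be identified.
- Denominator: SAP section 3 plans an accountability table by eyes and status, and baseline summaries by lens group for the Completed and Discontinued sets. SAP 5.3.2 plans percentages of eyes under the same four-group default. Lenses are worn in both eyes, so subjects are about half of eyes: 160/2 = 80 and 80/2 = 40 if all assigned subjects are dispensed.
- Result: 8 and 4 become 8/80 = 10% and 4/40 = 10%, and 6 and 6 become 6/80 = 7.5% and 6/40 = 15%, at one deficiency per subject.

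The quantities needed are therefore already in the planned output.

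**The case for a change.** The strongest case for a change is consistency at almost no cost. Among the visible endpoint summaries this one alone lacks percentages; even the Snellen categories of the primary endpoint have them (SAP 4.3.1). The eyes/subjects label in section 5 does not say which unit applies, and a packaging fault may belong to no eye at all. The accountability table is by eyes, so a subject N has to be derived. One sentence and one column would remove the ambiguity without new data.

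That is accurate, and adding n (%) and N would be good table design. It does not amount to a defect, for three reasons.

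- The SAP says counts and does not say of what. It cannot be held to have chosen event counts over subjects affected.
- The section 5 default already puts the lens groups side by side. What is missing is a printed rate; the comparison itself is there.
- Protocol 11.1 defines a deficiency as an inadequacy of the device, with examples such as a cloudy lens, an edge defect or a packaging fault. For product-level faults a count is a natural summary, and a percentage of subjects would not be a defect rate per lens. Preferring the subject as the unit is partly taste.

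The text directly after 5.3.3 is also blacked out. The visible paragraph reads as complete, but a general rule on percentages or denominators in the hidden part cannot be excluded.

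**Conclusion.** No change to the plan is needed. SAP 5.3.3 leaves out a detail that analysts fill sensibly: the group N beside each count and, if wanted, the number of subjects with at least one deficiency. Followed exactly as written, the plan still gives correct counts by lens group together with full listings.

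The most that can go wrong is a misreading by a factor of about two, by someone who compares raw counts without the group sizes. That factor assumes arms near 80 and 40, or 60 and 30 among completers. It would differ under uneven dropout, which the documents do not forecast. SAP 5.2 sets no safety hypothesis and the SAP's executive summary states no success criterion, so no test or decision depends on this table.
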